6.9.1 Monitoring and Management of Other Toxicities (e.g., Over-Arching Toxicities in Part B)

Corticosteroid therapy is known to cause mild to severe AEs that affect almost all body systems; however, the incidence of toxicity is dependent on multiple factors including the dose level and duration of treatment. Most common AEs known to occur with dexamethasone (low dose) may include hematological toxicity, i.e., anemia, thrombocytopenia, neutropenia (myelosuppression). Among nonhematological toxicity, i.e., diarrhea, nausea, vomiting, fatigue; systemic infection (specifically opportunistic); thromboembolic events including deep vein thrombosis and pulmonary embolism; and cutaneous rash have been reported; Investigators will be advised to refer to the local product label. Toxicities manifested by administration of dexamethasone in the expansion part of the study will be managed in accordance with the local medical practices and local labels; a guidance on the dose reduction during the study intervention period is provided ([Table 14A](#) and [Table 14B](#)). Albeit, dose reduction for toxicity deemed to be attributed to dexamethasone alone must be performed as clinically indicated. A deviation from the recommended dose reduction may be performed based on the clinical judgement of the study investigator and after discussion with the Sponsor Medical Monitor.

Since renal impairment is a common complication of MM, abnormalities in renal functions (new or worsening from Baseline) will be carefully monitored throughout the study. If decrease in estimated glomerular filtration rate is $> 25\%$ from Baseline or doubling of serum creatinine is observed, laboratory chemistry tests will be repeated within 72 hours from the initial finding in order to confirm the abnormal findings. The study participant will be evaluated thoroughly by the Investigator, i.e., physical examination, review of concomitant medication, etc. Upon recovery to \leq Grade 1 or pretreatment levels, study intervention may be resumed at the same or a lower dose, if appropriate, based on Investigator's clinical judgement and after discussion with the Sponsor Medical Monitor. Additionally, because of the common occurrence of renal involvement in MM, the use of nephrotoxic agents (e.g., NSAIDs) should be avoided throughout the study.

Grade 3 or 4 (Hematological or Nonhematological) Toxicities

If applicable, repeat laboratory tests in the local laboratory within 72 hours and then repeat tests twice a week until recovery to Grade 2 is observed. Thereafter, repeat laboratory tests as appropriate based on Investigator's clinical judgement.

For clinically evident Grade 4 toxicities occurring after DLT period, discontinuation of M3258 administration is advised. A decision on re-initiation of M3258 should only be considered after recovery of toxicity in question to \leq Grade 1 is observed within two weeks of discontinuation of M3258 treatment (if a laboratory parameter, recovery should be confirmed by a repeat test), and the dose of M3258 should be reduced by at least 1 dose level. When a dose reduction is required, no re-escalation of the dose will be allowed. If Grade 4 toxicity recurs upon resuming M3258, then administration of study treatment should immediately be discontinued. The decision to continue treatment should be discussed with the Medical Monitor and documented in the study records. In case of the occurrence of overlapping toxicities of M3258 and dexamethasone, the dose reduction of M3258 will occur first (see [Table 11](#), [Table 12](#), and [Table 13](#)). Dexamethasone dose should be reduced based on local product label or institutional guidelines only for toxicities which are deemed related to dexamethasone (for related toxicities and guidance on dose reduction, see [Table 14A](#) and [Table 14B](#)).

In the event of new or worsening pulmonary symptoms, a prompt diagnostic evaluation and involvement of a pulmonologist should be considered. Participants will be treated according to institutional standards. Since low-grade pulmonary toxicities (Grade 1-2), such as dyspnea and cough, manifest as symptoms of diverse underlying etiologies, the study investigators should bear high suspicion for study treatment-induced pulmonary injury. The study investigator will also be required to discuss any grade pulmonary toxicity with the Sponsor medical representative. Re-initiation of M3258 must be discussed with the Sponsor medical representative. The benefit/risk balance should be considered prior to continuing M3258 therapy.

The adverse events suggestive of lung toxicity with Grade ≥ 3 irrespective of attributability will be reported as SAEs throughout the study.

Grade 4 toxicity should always be reported to the Sponsor as a SAE in expedited manner, within 24 hours of awareness.

Treatment cycles with M3258 -/+ combination with dexamethasone will be repeated every 21 or 28 days; hence, for a cycle of treatment to begin, the participant's blood ANC must be \geq 1,000 mm³ and the platelet count must be \geq 75,000 mm³. Additionally, all other toxicities considered to be related to study intervention must have resolved to \leq Grade 1 or to the participant's Baseline value.

If the participant fails to meet the above-cited criteria for treatment, re-initiation of the next cycle of treatment should be delayed for one week. At the end of which, the participant should be re-evaluated to determine whether the criteria for re-treatment have been met. If a delay in the initiation of the next cycle of more than two weeks is required because of incomplete recovery from toxicity, then this event should be considered a DLT. If toxicity does not resolve by two weeks, then the participant should be discontinued from the study. This decision will be made in the context of emerging clinical data and in consultation with Sponsor Medical Responsible. If, in the opinion of the Investigator and the Sponsor Medical Responsible, it is in the participant's best interest to continue the treatment with M3258 -/+ combination with dexamethasone, the study intervention will only be resumed after recovery from toxicity to \leq Grade 1 or Baseline values. Additionally, the dose of study intervention should be reduced by at least 1 dose levels. If the DLT recurs upon resuming study intervention at a lower dose, the study intervention should immediately be discontinued. For the first study cohort, no dose reduction will be allowed.

7

Discontinuation of Study Intervention and Participant Discontinuation/Withdrawal

7.1

Discontinuation of Study Intervention

Stopping Rules for Individual Participants:

The Investigator must consider discontinuation of study intervention for abnormal liver function when a participant meets one of the conditions outlined in Section 6.6 or if the Investigator believes that it is in best interest of the participant.

All events of ALT \geq 3 \times ULN and bilirubin \geq 2 \times ULN ($> 35\%$ direct bilirubin) or ALT $>$ 3 \times ULN and international normalized ratio (INR) $>$ 1.5, if INR measured, may indicate potential severe liver injury (possible Hy's Law) and must be reported as an AE and SAE.

If a clinically significant finding in ECG recording is identified (including, but not limited to changes from Baseline in QT interval corrected using Fridericia's formula [QTcF]) after enrollment, the Investigator or qualified designee will determine if the participant can continue in the study and if any change in participant management is needed. This review of the ECG printed at the time of collection must be documented. Any new clinically relevant finding should be reported as an AE.

The SoA (Table 1 and Table 2 for Part A; Table 3 and Table 4 for Part B) specifies the data to collect at study intervention discontinuation and Follow-Up, and any additional evaluations that need to be completed.

If a participant's study intervention must be discontinued, this will not result in automatic withdrawal of the participant from the study and the participant should be assessed at the End-of-Treatment visit and Safety Follow-Up visit.

A participant's study intervention should be discontinued if:

- The Investigator believes that for safety reasons (eg, AE) it is in the best interest of the participant to discontinue study intervention.
 - The participant becomes pregnant.
 - The participant (or the participant's legally authorized representative) withdraws consent for administration of study intervention.
 - The participant's dose is held for more than 5 days per cycle, or if ≥ 6 consecutive planned doses of M3258 are missed for reasons other than toxicity unless, upon consultation with the Sponsor and the review of safety and efficacy, continuation is agreed upon.
 - The participant experiences disease progression.

Safety Stopping Rules for Study Intervention in Part B:

Unacceptable toxicity in the expansion cohort is defined as AEs that meet the DLT criteria regardless of when they occur during treatment (as defined in Section 6.6). The following stopping rules for unacceptable toxicity apply:

- ≥ 5 participants with observed DLT criteria out of 12 evaluable participants treated on the same dose.
- ≥ 7 participants with observed DLT criteria out of 18 evaluable participants treated on the same dose.
- ≥ 9 participants with observed DLT criteria out of 24 evaluable participants treated on the same dose.
- The chance is $>80\%$ that the true DLT rate is $\geq 30\%$ (based on Bayes model).

If at any time in the expansion cohort, the number of unacceptable toxicity events indicate that there is a risk of safety to the participants (i.e., if any of the above boundary is met), accrual to the cohort will be paused and the SMC will meet to determine whether further enrollment should be halted taking into account feedback from study Investigators. In this case, the SMC will decide whether participants still on treatment and tolerating the treatment can stay on treatment or whether treatment needs to be dose reduced or withdrawn. The HA will be notified of the SMC decision.

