8.3 Adverse Events and Serious Adverse Events

The definitions of an AE and a SAE are in [Appendix 5](#).

8.3.1 Time Period and Frequency for Collecting Adverse Event and Serious Adverse Event Information

The AE reporting period for safety surveillance begins when the participant is initially included in the study (date of first signature of informed consent/date of first signature of first informed consent) and continues until the 30-Day Follow-Up Safety Visit.

Any SAE assessed as related to study intervention must be recorded and reported, as indicated in [Appendix 5](#), whenever it occurs, irrespective of the time elapsed since the last administration of study intervention.

The method of recording, evaluating, and assessing causality of AEs (including SAEs) and the procedures for completing and transmitting SAE reports are in [Appendix 5](#).

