The Investigator is required to grade the severity or toxicity of each AE.

Investigators will reference the National Cancer Institute - Common Terminology Criteria for AEs (NCI-CTCAE), version 5.0 (publication date: 27 Nov 2017), a descriptive terminology that can be used for AE reporting.

A general grading (severity/intensity, hereafter referred to as severity) scale is provided at the beginning of the above referenced document, and specific event grades are also provided.

If the severity for an AE is not specifically graded by NCI-CTCAE, the Investigator is to use the general NCI-CTCAE definitions of Grade 1 through Grade 5, using his or her best medical judgment.

The 5 general grades are:

Grade 1 or Mild

Grade 2 or Moderate

Grade 3 or Severe

Grade 4 or Life-threatening

Grade 5 or Death

Any clinical AE with severity of Grade 4 or 5 must also be reported as an SAE. However, a laboratory abnormality of Grade 4, such as anemia or neutropenia, is considered serious only if the condition meets one of the serious criteria specified below.

If death occurs, the primary cause of death or event leading to death should be recorded and reported as an SAE. "Fatal" will be recorded as the outcome of this specific event and death will not be recorded as separate event. Only, if no cause of death can be reported (e.g., sudden death, unexplained death), the death per se might then be reported as an SAE.

Investigators must assess the severity of AEs per the Qualitative Toxicity Scale, as follows:

Mild:

The participant is aware of the event or symptom, but the event or symptom is easily tolerated.

Moderate:

The participant experiences sufficient discomfort to interfere with or reduce his or her usual level of activity.

Severe:

Significant impairment of functioning: the participant is unable to carry out his or her usual activities.

Investigators must also systematically assess the causal relationship of AEs to study intervention (including any other non-study interventions, radiation therapy, etc.) using the following definitions. Decisive factors for the assessment of causal relationship of an AE to the M3258 include, but may not be limited to, temporal relationship between the AE and the M3258, known side effects of M3258 or dexamethasone, medical history, concomitant medication, course of the underlying disease, and study procedures.

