Unrelated: Not reasonably related to the study intervention. AE could not medically (pharmacologically/clinically) be attributed to the study intervention under study in this clinical study protocol. A reasonable alternative explanation must be available.

Related: Reasonably related to the study intervention. AE could medically (pharmacologically/clinically) be attributed to the study intervention under study in this clinical study protocol.

Abnormal Laboratory Findings and Other Abnormal Investigational Findings

Abnormal laboratory findings and other abnormal investigational findings (e.g., on an ECG trace) should not be reported as AEs unless they are associated with clinical signs and symptoms, lead to study intervention discontinuation or are considered otherwise medically important by the Investigator. If a laboratory abnormality fulfills these criteria, the identified medical condition (e.g., anemia or increased ALT) must be reported as the AE rather than the abnormal value itself.

Serious Adverse Events

An SAE is any untoward medical occurrence that at any dose:

- Results in death
- Is life-threatening. Life-threatening refers to an event in which the participant is at risk of death at the time of the event, not an event that hypothetically might have caused death if it was more severe.
- Requires inpatient hospitalization or prolongs an existing hospitalization
- Results in persistent or significant disability or incapacity
- Is a congenital anomaly or birth defect
- Is otherwise considered to be medically important. Important medical events that may not result in death, be life-threatening, or require hospitalization may be considered as SAEs when, based upon appropriate medical judgment, they may jeopardize the participant or may require medical or surgical intervention to prevent one of the outcomes listed above. Examples of such events include allergic bronchospasm

requiring intensive treatment in an emergency room or at home, blood dyscrasias or convulsions that do not result in inpatient hospitalization, or the development of drug dependency or drug abuse.

For the purposes of reporting, any suspected transmission of an infectious agent via a study intervention is also considered an SAE, as specified below for reporting SAEs, AESIs and DLTs.

Events that Do Not Meet the Definition of an SAE

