15.2 Adverse Events

AEs will be analyzed among the SAF analysis set and presented by regimen and dose (in increasing order) and summarized. Only participants counts will be presented with frequency.

Treatment-emergent adverse events (TEAE) are those events with onset dates occurring within the on-treatment periods as defined in section [9.4](#).

- **Related Adverse Events:** AEs with relationship missing, unknown or yes. Relationship is judged separately for M3258, and dexamethasone.
- **SAEs:** Serious adverse events (as recorded on the AE eCRF page, Serious Adverse Event = 'Yes').
- **AEs Leading to Treatment Discontinuation:** AEs leading to permanent discontinuation of study treatment (as recorded on the AE eCRF page, Action taken with study treatment = 'Drug withdrawn'). Treatment discontinuation is recorded separately for M3258, and dexamethasone.
- **AEs Leading to Death:** AEs leading to death (as recorded on the AE eCRF page, Outcome = 'Fatal').

All analyses described in Section [15.2](#) will be based on TEAEs if not otherwise specified.

TEAEs will be summarized by number and percentage of participants with at least one TEAE in the category of interest, by primary MedDRA and PT (both sorted alphabetically), unless otherwise stated. Each participant will be counted only once within each SOC or PT. If a participant experiences more than one AE within a SOC or PT for the same summary period, only the AE with the strongest relationship or the worst severity, as appropriate, will be included in the summaries of relationship and severity.

The severity of adverse events will be graded using the NCI-CTCAE version 5.0, except where CTCAE grades are missing. No imputation of missing grades will be performed.

Adverse events will be coded according to the latest MedDRA version at the time of the data cut-off.

Incomplete AE-related dates will be handled as defined in section [9.5](#).

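### Section 6.9.1 and Appendix 5 classify the same Grade 4 laboratory adverse event differently for seriousness, and the SAP carries the site's choice into the serious TEAE counts

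*Protocol*

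**What the plan says.** Protocol Section 6.9.1, under the heading "Grade 3 or 4 (Hematological or Nonhematological) Toxicities", states: "Grade 4 toxicity should always be reported to the Sponsor as a SAE in expedited manner, within 24 hours of awareness". It makes no exception for laboratory events.

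Appendix 5 separates clinical from laboratory events. For clinical events the rule is: "Any clinical AE with severity of Grade 4 or 5 must also be reported as an SAE". For laboratory events it is: "a laboratory abnormality of Grade 4, such as anemia or neutropenia, is considered serious only if the condition meets one of the serious criteria", which the appendix then lists.

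Appendix 5 also limits when a laboratory finding is an AE at all. Such findings "should not be reported as AEs unless they are associated with clinical signs and symptoms, lead to study intervention discontinuation", or are judged medically important by the investigator.

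Section 8.3 points to the appendix: "The definitions of an AE and a SAE are in" Appendix 5. It does not say that the appendix overrides Section 6.9.1.

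SAP Section 15.2 defines SAEs by the site's entry, "as recorded on the AE eCRF page, Serious Adverse Event = 'Yes", and states no step to harmonise that entry across sites.

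**The concern.** A site that reads Section 6.9.1 literally and a site that reads Appendix 5 literally are both following the protocol, yet they can flag the same laboratory event differently. The study is multicenter and the dose groups are small. A difference in serious TEAE counts between dose levels could therefore reflect which section the enrolling site followed rather than the drug. Seriousness is also one of the elements that make an event a SUSAR (Section 8.3.4), so expedited reporting could differ as well.

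**Working it through.** The plan states no figure to reproduce. The check is a comparison of the two texts, a trace of the flag into the outputs, and a short scale illustration.

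**1. Where the two rules differ**, for an event already recorded as an AE:

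| Event | Section 6.9.1 | Appendix 5 |
|---|---|---|
| Grade 4, clinical | SAE | SAE |
| Grade 4, laboratory, seriousness criterion met | SAE | SAE |
| Grade 4, laboratory, no criterion met | SAE | Not serious |

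Only the third row is in conflict. Section 6.9.1 confines its advice on stopping M3258 to Grade 4 toxicities that are clinically evident, but its SAE sentence carries no such limit.

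**2. Whether the third row can contain any events.** The Appendix 5 filter removes laboratory findings that are asymptomatic, cause no discontinuation and are not medically important. Two kinds of event still pass:
- *DLTs.* Section 6.6 counts Grade 4 hematologic AEs as DLTs, with listed exceptions, and says participants with a DLT stop treatment permanently. Discontinuation makes the finding an AE. Appendix 5 tells sites to report serious DLTs as SAEs, which presupposes that some DLTs are not serious.
- *Liver enzymes.* Appendix 6 has ALT or AST above 3 × ULN recorded as an AE whether or not there are symptoms. It calls for an SAE only when bilirubin is also raised and no other cause has been found.

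The route through medical importance is different. Appendix 5 also lists medical importance as a seriousness criterion and gives blood dyscrasias as an example. For those events the two rules can agree.

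**3. Where the flag goes.**
- *Affected (SAP Sections 15.2.1 and 15.3.2):* the serious TEAE row, the row for serious TEAEs related to M3258, the registry table of TEAEs without SAEs (where an event leaves as it enters the serious count), and the SAE listings.
- *Not affected:* the Grade ≥ 3 and Grade ≥ 4 TEAE rows and the laboratory CTCAE tables, which use grade, and the DLT counts, which use the investigator's DLT flag and the SMC decision.
- *Part A primary endpoint:* it covers any AE, serious or nonserious, so it does not change with the flag.

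**4. Scale.** Protocol Section 9.2 plans cohorts of 3 and anticipates two dose levels of 3 and two of 6, so 2 × 3 + 2 × 6 = 18 participants. Assume one participant whose only candidate serious event falls in the third row. The serious TEAE proportion then differs between the two rules by 1/n:
- n = 3: 1/3 = 33.3 percentage points
- n = 6: 1/6 = 16.7 points
- n = 18: 1/18 = 5.6 points

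**The case against.** The strongest reply is that a hierarchy is implied. Section 8.3 places the SAE definition in Appendix 5, and Section 8.3.1 sends recording and reporting procedures there, whereas Section 6.9.1 is about managing toxicity. Its sentence could then be read as setting a reporting route, as Section 8.4 does for overdose. This has some force, but the hierarchy is never stated. Section 8.4 refers to an SAE report form, while Section 6.9.1 says the event is reported as an SAE.

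A second reply is that the information needed to sort out individual cases is already collected. Appendix 5 requires seriousness criteria to be documented, the SAP lists every AE with grade and SAE status, and the planned numbers are small enough to read case by case. That stands, and it limits the damage. It does not make the tabulated counts or the registry table comparable.

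A third reply is that the Appendix 5 filter leaves few events in conflict. It does narrow the problem: not every Grade 4 laboratory value is caught. Events that become AEs through discontinuation or through Appendix 6 remain.

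**Conclusion.** The inconsistency is real but confined to Grade 4 laboratory events that are recorded as AEs and meet no seriousness criterion. It affects the serious TEAE rows, the registry table and the SAE listings, and possibly expedited reporting. The analyses are descriptive, and no dose decision rule uses the flag.

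The documents give no rate for such events, so the actual effect cannot be computed. The 33, 17 and 5.6 points are per reclassified participant and assume no other SAE in that participant. Counting is per participant, so anyone with another SAE is already in the numerator.

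A reader might go further in two ways that the documents do not support:
- *That the Part A primary endpoint is distorted.* It is not, because it counts AEs of either kind. Treatment-emergent SAEs are a separate primary endpoint only in Part B, which the SAP says will not be done.
- *That the distortion must be large because Grade 4 cytopenias are frequent in this disease.* Neither document gives a frequency, and the filter removes asymptomatic laboratory findings unless they lead to discontinuation or are medically important.

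**What to change.** Reconcile Section 6.9.1 and Appendix 5 so that one SAE rule applies to Grade 4 laboratory events, and cross-refer from one to the other.

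In SAP Section 15.2.1, keep the serious TEAE row and add a second one that leaves out events whose only basis is a Grade 4 laboratory value with no documented seriousness criterion. Appendix 5 already requires the criteria to be recorded. Enrollment stopped before the current SAP version, so this row is the part that helps the report most. If some sites entered medical importance merely to satisfy Section 6.9.1, the row would not remove those events. Showing the recorded criterion for Grade 4 laboratory SAEs in the existing SAE listing would reveal them.

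The cost is a wording change in the protocol and one extra table row.
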